Each session was accompanied by the consumption of a flavor matched beverage. This beverage contained either 0 or 30 grams of hydrolyzed collagen (HC), combined with vitamin C. The 0 g beverage also contained vitamin C and was matched with the 30 g beverage for caloric content by the inclusion of maltodextrin.

Post-intervention, participants returned to the laboratory 72 hours after their final training session to repeat all baseline assessments.

Arm 2:

Training and nutrition intervention for middle-aged female participants (aged 35 - 59 years), who consumed hydrolyzed collagen (HC) or a placebo beverage with progressive resistance training.

Arm 2 Description:

This arm was identical to Arm 1 (male cohort), however it was conducted in middle-aged females.

1. Period

Arm 1: Participants were recruited from university staff, and sports and leisure clubs. Recruitment began in June 2021 and data collection was completed in December 2021.

Arm 2: Participants were recruited from university staff and sports clubs. Recruitment began in March 2023 and data collection was completed in June 2023.

2. Baseline Characteristics

Arm 1: 20 middle-aged males (mean \pm SD; age, 47 ± 5 years, body mass, 81 ± 12 kg; height 178 ± 7 cm)

Arm 2: 22 middle-aged females (mean \pm SD; age 37 ± 2 years, body mass, 69 ± 8 kg, 168 ± 4 cm)

- Age
 - > 35 and < 59 years;
- Sex
 - Male and female
- Ethnicity
 - Race and ethnicity information not collected
- Region of enrolment
 - Arm 1: Carlow, Ireland
 - Arm 2: Dublin, Ireland

3. Outcome measure information

Table 1. Outcome measures by study arm

	Number of participants analyzed	Description	Time frame
Primary	42 (Arm1: 20; Arm 2: 22)	m. vastus lateralis thickness (in millimeters)	Data analyzed between January 2022 & September 2023
Primary	43 (Arm1: 20; Arm 2: 22)	m. vastus lateralis fascicle pennation angle (in degrees)	Data analyzed between January 2022 & September 2023
Primary	43 (Arm1: 20; Arm 2: 22)	Patellar tendon cross sectional area (in squared millimeters) at 3 regions along the tendon length	Data analyzed between January 2022 & September 2023
Primary	43 (Arm1: 20; Arm 2: 22)	Bilateral vertical countermovement jump height (in centimeters)	Data analyzed between January 2022 & September 2023
Primary	Arm 1: 20	Patellar tendon stiffness (in Newtons per millimeter)	Data analyzed between January 2022 & September 2023

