Primary	Arm 1: 20	Knee extensor maximal isometric torque (in Newton meters)	Data analyzed between January 2022 & September 2023
Primary	Arm 1: 20	Knee extensor rate of torque development (in Newton meters per second)	Data analyzed between January 2022 & September 2023
Primary	Arm 1: 20	Barbell back squat 10-repetition maximum (in kilograms)	Data analyzed between January 2022 & September 2023
Primary	Arm 1: 20	Bilateral horizontal broad jump distance (in centimeters)	Data analyzed between January 2022 & September 2023
Primary	Arm 2: 22	Lower limb maximal isometric force (in Newtons)	Data analyzed between July 2023 & September 2023
Primary	Arm 2: 22	Lower limb isometric rate of force development (in Newtons per second)	Data analyzed between July 2023 & September 2023
Primary	Arm 2: 22	20-metre sprint time (in seconds)	Data analyzed between July 2023 & September 2023

Statistical Analyses Plan (SAP)

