In Arm 1, data from 20 male participants were analyzed and in Arm 2, data from 22 female participants were analyzed. The analyses of data collected from each arm were performed independently. All variables were ratio data, and normal distribution was assessed using the Shapiro-Wilk test, along with visual inspections of histograms, Q-Q plots, and box plots. All data met the assumptions of the parametric statistical analyses used in the study. Independent t-tests were used to assess differences between groups (COL, collagen and PLA, placebo) at baseline for all measures. The two-way analysis of variance (ANOVA) was performed on all measures taken at baseline and after the intervention to assess the main effects of group (COL vs PLA), time (pre- vs post- intervention), and any group \times time interactions. The only exceptions to this were for patellar tendon cross-sectional area, and rate of torque/force development. For the patellar tendon cross-sectional, a three-way ANOVA was used to assess main effect of location (along the length of the tendon), and any interactions between location, time (pre- to post- intervention) and group (COL vs PLA). Likewise for rate of torque/force development, a three-way ANOVA was used to assess main effect of time-window (0 – 50, 50 – 100, 100 – 150 ms after the onset of torque/force), time (pre- to post- intervention) and group (COL vs PLA) and any interactions between time-window, time and group. When significant main effects or interaction effects were observed, paired t-tests were used for post hoc pairwise comparisons. The level of statistical significance was set at $P < 0.05$

4. Adverse Event Information

During data collection period, any adverse event such as all-cause mortality or serious adverse event did not occur.

5. Certain Agreements

Are all PIs Employees of Sponsor? Yes

Results Disclosure Restriction on PI(s)?

No

6. Results Point of Contact

[name] Research Institute for Sport and Exercise Sciences, Liverpool John Moores

University [contact]; E-mail: [contact]

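### For tendon cross-sectional area and rate of torque/force development, the stated follow-up to a significant three-way interaction (paired t-tests) cannot show at which location or time-window collagen and placebo differ

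*Combined protocol and SAP*

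**What the plan says.** The Statistical Analyses Plan (SAP) section uses a two-way ANOVA (group, time, group x time) for most measures. The exceptions are tendon cross-sectional area (CSA) and rate of torque or force development. For CSA, "a three-way ANOVA was used to assess main effect of location (along the length of the tendon), and any interactions between location", time and group are examined. For rate of torque or force development the third factor is time-window, with three windows of 50 ms, "and any interactions between time-window, time and group".

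The follow-up rule is the same for every model: "When significant main effects or interaction effects were observed, paired t-tests were used for post hoc pairwise comparisons". The only t-test between groups is at entry: "Independent t-tests were used to assess differences between groups (COL, collagen and PLA, placebo) at baseline for all measures".

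Table 1 lists the three affected outcomes, all labelled primary: "Patellar tendon cross sectional area (in squared millimeters) at 3 regions along the tendon length" (both arms), "Knee extensor rate of torque development (in Newton meters per second") (Arm 1) and "Lower limb isometric rate of force development (in Newtons per second") (Arm 2). On the two arms, the SAP says: "The analyses of data collected from each arm were performed independently".

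**The concern.** The design has parallel groups, so COL against PLA is a comparison between different people. A paired t-test, as usually understood, compares measurements within the same people: before with after, or one location with another. Suppose the three-way term is significant. The natural next question is which tendon region or which time-window responds differently under collagen. The plan names no test that answers it.

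At stake is any statement that collagen acted at a particular region or in a particular time-window. Such a statement would have no planned between-group test behind it, and a within-group test is a poor substitute.

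**Working it through.** **Scope, counted from Table 1 and the SAP.** There are 12 outcomes: 9 with a two-way ANOVA and 3 with a three-way ANOVA. Arm 1 has 7 two-way + 2 three-way analyses (CSA, rate of torque development). Arm 2 has 5 + 2 (CSA, rate of force development). Total 9 + 7 = 16, of which 4 are three-way.

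**What each term tests.** Let D_j be the mean pre-post change in COL minus that in PLA at level j (location or window), j = 1, 2, 3.
- Two-way model: there is a single D. Group x time tests D = 0, which is the same as an independent t-test on change. Nothing is missing.
- Three-way model: group x time tests that the average of D_1, D_2, D_3 is 0. The three-way term tests D_1 = D_2 = D_3. Both compare the groups, but neither tests D_j = 0 at a given j.
- Paired t-test: mean change / (s/√n) within one set of people. D_j does not appear in it.
- The missing contrast, with n per group: t_j = D_j / (s_j √(2/n)), on 2n − 2 degrees of freedom.

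**No figure to reproduce.** The documents give no sample size calculation, SD, expected gain or split by group. What follows is illustrative.

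**Assumptions.** 10 per group (half of the 20 men), normal changes with SD 1, equal correlation of 0.2-0.8 between locations, two-sided 0.05. A real collagen effect of 0.8, 1.0 or 1.5 SD exists at one location only, and the three-way F (2 and 2 x 2 x 9 = 36 df) is significant. Both groups share a training gain at all locations.

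**If paired tests split by group were used to locate the effect**, this is how frequently a location with no collagen effect would show a significant gain in COL and none in PLA:

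| Shared gain (SD) | Split paired tests, wrong location |
|---|---|
| 0 | about 4% |
| 0.3 | 16-19% |
| 0.6-0.8 | 31-37% |
| 1.2 | 9-12% |
| 1.5 | about 2% |

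Holm-adjusted COL-PLA contrasts name a wrong location in 3-8%.

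**Missing the true location.** Split tests miss it in 7-22% (gain 0.3), 22-40% (0.6), 44-62% (0.8) and over 80% (1.2-1.5). Holm contrasts miss it in 48-74%, 36-62% and 14-25% for effects of 0.8, 1.0 and 1.5 SD. The contrasts are therefore not always more sensitive.

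**Multiplicity of the contrasts.** Three unadjusted tests, if independent: 1 − 0.95³ = 14.3%. At 0.05/3 = 0.0167 each: 1 − (1 − 0.0167)³ = 4.9%.

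**Power of the contrasts** (noncentral t, noncentrality d√(n/2)). With 10 per group and d = 1.0, power is 56% unadjusted and 37% at 0.0167. The difference detectable with 80% power is 1.32 SD at 0.05 and 1.57 SD at 0.0167; with 11 per group it is 1.26 and 1.49 SD.

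With Holm and d = 1.0, power to name the location is 32-37% if either a significant group x time or a significant three-way term opens the contrasts. If only the three-way term does, it is P(three-way significant) x (1 − miss rate). A re-run gave 0.40 x 0.63 = 25%, 0.59 x 0.50 = 30% and 0.95 x 0.38 = 36% at correlations of 0.2, 0.5 and 0.8.

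**The case against.** **The trial's question is already tested.** Research question 1 in the Brief Summary asks whether collagen changes tendon properties more than training by itself, not at which region. A reader might infer that the plan leaves it without a between-group test. It does not: group x time and the three-way term are both between-group tests of change. No regional or window-specific hypothesis is stated, and the gap matters only after a significant three-way term. This objection stands and limits the point to localisation.

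**The misuse is hypothetical.** A reader might also infer that the investigators ran paired tests in each group and took a gain in COL alone as benefit. The SAP says neither. Nor does it say that a significant time effect was followed by tests split by group; with two time points a pooled pre-post comparison is the ordinary follow-up, and it cannot produce that pattern. The percentages for split tests describe a stand-in procedure, and the excess over Holm contrasts is confined to intermediate gains. Nothing in the documents places the trial there. This stands too.

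**Paired could mean matched pairs.** The Arm 1 Description says that men were matched in pairs before allocation, and Arm 2 is described as identical. A paired COL-PLA test is therefore possible. But no such analysis is described, and the baseline group comparison uses independent t-tests. This shows that the wording needs clarifying; it does not fill the gap.

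**The remedy has little power.** This is true, as the figures above show. The gain is a test that answers the right question and names few wrong locations, not greater sensitivity.

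**Conclusion.** The point holds for 4 of 16 analyses and is minor. As written, the follow-up rule cannot show where COL and PLA differ after a significant three-way interaction, because no COL-PLA contrast of change by location or time-window is named. That conclusion rests on the SAP wording and on reading paired t-tests as within-person tests.

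It does not extend to the nine two-way outcomes, where group x time is itself the COL-PLA test of change. Nor does it mean that the overall between-group question goes untested.

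The cost of using split paired tests instead is uncertain: about 2% to 37% wrong locations over shared gains of 0-1.5 SD, against 3-8% with Holm contrasts. It depends on the assumed 10 per group, equal SDs and correlations, and a gain that the documents do not give.

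**What to change.** In the four three-way analyses, after a significant three-way interaction, replace the paired t-tests as the between-group follow-up with COL-PLA contrasts of pre-post change at each location or time-window. Report each with a 95% CI and a stated multiplicity adjustment; Holm is one option. State that any collagen claim rests on group x time or the three-way term, report within-group changes descriptively with CIs, and say what each remaining paired test compares. The nine two-way outcomes need no extra test.

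The cost is SAP wording and a re-run of four analyses on existing data. Table 1 puts the end of analysis in September 2023 and the document is dated 04/22/2024, so the new contrasts must be labelled post hoc. The main downside is low power to name a location: for a 1.0 SD local effect with Holm, about 32-37% if either interaction involving group opens the contrasts, and about 25-36% if only the three-way term does. A non-significant contrast should not be read as absence of an effect at that location.

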The Effect of Vitamin C-enriched Collagen Combined with Resistance Training on Muscle-tendon Unit Properties in Middle-aged Men and Women

Study protocol, statistical analysis plan and informed consent form.

Document date: 04/22/2024

1. Participant Flow

[figure not shown]

Figure 1. Flowchart of participant recruitment and intervention timeline (males).

[figure not shown]

Figure 2. Flowchart of participant recruitment and intervention timeline (females).

Study Protocol

Brief Summary:

The aim of this clinical trial is to investigate the longitudinal effects of hydrolyzed collagen ingestion combined with resistance training on muscle-tendon unit structure and function in middle-aged males and females.

The main research questions this clinical trial aims to answer are:

1. Does resistance training with hydrolyzed collagen ingestion lead to greater changes in tendon properties than resistance training alone in middle-aged health men and women?
2. Does resistance training with hydrolyzed collagen ingestion lead to greater changes in muscle size than resistance training alone?
3. Does resistance training with hydrolyzed collagen lead to greater increases in strength and power compared to resistance training alone in middle-aged, healthy men and women?

Participants will be randomly assigned to collagen or placebo groups. Participants will perform 24 sessions of high intensity resistance training across 12-weeks. Alongside each training session, participants will consume a beverage containing hydrolyzed collagen or maltodextrin, with both beverages containing vitamin C.

Researchers will compare the collagen and placebo groups to see if there would be beneficial effects on changes in muscle and tendon that are greater than resistance training alone. To achieve this, an dynamometry will be used to assess lower limb strength and ultrasound will be used to measure the morphological, mechanical, and material properties of the patellar tendon, as well the size and architecture of the vastus lateralis muscle.

Detailed Description:

Healthy, active, middle-aged men and women will ingest a beverage containing 30 g of hydrolyzed collagen with 50 mg of vitamin C or a calorie matched beverage (maltodextrin), also with 50 mg of vitamin C combined with high-volume, high-intensity resistance training for the lower body on 2 - 3 occasions per week for 8-12 weeks.

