The aim of this study was to investigate the effect of combining hydrolyzed collagen with resistance training in middle-aged men and women. If supplementation with hydrolyzed collagen leads to a greater change in tendon size, stiffness, and Young's modulus than resistance training alone, this will allow us to recommend this type of intervention to young athletes seeking to improve tendon health and/or athletic performance. This is the first study to investigate the combination of hydrolyzed collagen supplementation with resistance training in middle-aged men and women. If supplementation with hydrolyzed leads to greater improvements in tendon size, stiffness, strength and/or power, this

will allow us to recommend this type of intervention to middle-aged athletes/trainees seeking to improve tendon health, reduce injury risk, or enhance athletic performance.

The experimental design of both arms will be the same, however Arm 1 will be health, middle-aged male participants and Arm 2 will be health, middle-aged female participants.

Arm/Group Information

Arm 1:

Training and nutrition intervention for middle-aged male participants (aged 35 - 59 years) who consumed hydrolyzed collagen (HC) or a placebo beverage with progressive resistance training.

Arm 1 Description:

This arm was designed as a double-blind, randomized control study with parallel groups. Middle-aged, recreationally trained men, pair-matched by age, body mass, height and baseline strength, were randomly allocated to the collagen (COL) or placebo (PLA) group.

During their initial laboratory visit, participants were screened and provided with a 3-day food diary and its completion instructions. Before undergoing baseline assessments, participants engaged in a warm-up routine that included 5 minutes of low-intensity jogging followed by 5 minutes of dynamic stretching. The baseline assessments of lower limb muscle-tendon unit properties, lower limb strength and power were conducted at the same time of day to mitigate any potential circadian effects.

The 12-week progressive lower-limb resistance training program comprised a combination of supervised and home-based training sessions focused on overloading the quadriceps femoris muscle-tendon unit. Training loads were adjusted weekly based on the prior session's performance using a linear progression model.

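### The post hoc rule lets a training (time) effect alone lead to unadjusted within-group paired tests, which can show improvement with collagen but not placebo when the group × time interaction is null

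*Combined protocol and SAP*

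**What the plan says.** The section headed Statistical Analyses Plan (SAP) analyses men and women separately: "In Arm 1, data from 20 male participants were analyzed and in Arm 2, data from 22 female participants were analyzed". For most outcomes a two-way ANOVA is used "to assess the main effects of group (COL vs PLA), time (pre- vs post- intervention") and their interaction. Patellar tendon cross-sectional area has location as a third factor, and rate of torque or force development has time-window as a third factor, with three levels each.

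The follow-up rule is one sentence: "When significant main effects or interaction effects were observed, paired t-tests were used for post hoc pairwise comparisons". The significance level is 0.05. The section does not name the pairs, adjust for the number of comparisons, or say which result decides whether collagen worked.

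The questions are in the Brief Summary of the Study Protocol. All three concern a difference in change between groups; the second reads: "Does resistance training with hydrolyzed collagen ingestion lead to greater changes in muscle size than resistance training alone".

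**The concern.** In a two-group, pre-post design a time main effect says that people changed on average. It says nothing about whether collagen users changed more. The programme is progressive and aimed at overloading the quadriceps muscle-tendon unit, so a time effect is likely in both groups.

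Under the rule as written, that effect alone opens paired t-tests. With two time points, a pooled pre-post test would largely repeat the main effect. A paired test is also not the natural comparison of collagen with placebo: participants were pair-matched before allocation, but the SAP compares the groups at baseline with independent t-tests and treats group as an ordinary factor. The paired comparison left that adds information is pre-post within each group.

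If one such test is significant and the other is not, that is no evidence that the groups differ. It is nevertheless easily reported as improvement with collagen but not with placebo. The Detailed Description ties tendon, strength and power findings to recommendations for athletes, so the reading matters.

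**Working it through.** The plan gives no power or error figure for the post hoc step, so there is nothing to reproduce. The check asks how often the misleading pattern appears when collagen does nothing.

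**Inputs from the documents.** Analysed: 20 men and 22 women, arms separate. Level 0.05. Trigger and type of test as quoted.

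**Assumptions.** Two-sided tests. Equal split, n = 10 per group in men and 11 in women; group sizes are not stated, but the Arm 1 Description says men were "pair-matched by age, body mass, height and baseline strength, were randomly allocated to the collagen (COL) or placebo (PLA) group". Normal change scores with the same true mean in both groups. The training effect d (mean change divided by SD of change) is not in the documents, so a range is shown.

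**Step 1: exact check without the gate.** Within one group, t = mean change ÷ (SD ÷ √n) on n − 1 df. Power p comes from the noncentral t with noncentrality d√n. The groups are independent, so P(collagen significant, placebo not) ≈ p(1 − p). At n = 10, d = 0.7: noncentrality 0.7 × √10 = 2.21, p = 0.506, and 0.506 × 0.494 = 0.250. This product cannot exceed 0.25.

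**Step 2: apply the rule.** The simulation used 200,000 trials per setting. Write m_C and m_P for the mean changes and s for the pooled SD, with 2n − 2 df:

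- time: t = [(m_C + m_P)/2] ÷ [s√(1/(2n))]
- group × time: t = (m_C − m_P) ÷ [s√(2/n)]

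The pattern counted is: time significant, group × time not significant, collagen improved significantly, placebo not significant. A group main effect was not used as a trigger; including it would add a little.

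| d | Power in one group, n = 10 | Time significant, n = 10 | Pattern, n = 10 | Pattern, n = 11 |
|---|---|---|---|---|
| 0 | 2.5% | 5.0% | 0.7% | 0.7% |
| 0.3 | 13.4% | 24.6% | 6.9% | 7.6% |
| 0.5 | 29.2% | 56.1% | 15.8% | 17.1% |
| 0.7 | 50.8% | 84.3% | 21.5% | 21.6% |
| 0.9 | 71.7% | 96.7% | 18.3% | 15.8% |
| 1.0 | 80.3% | 98.8% | 14.1% | 11.5% |
| 1.2 | 92.0% | 99.9% | 6.5% | 4.3% |
| 1.5 | 98.7% | 100.0% | 1.0% | 0.5% |

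At n = 10, d = 0.7, the two steps link as follows. The ungated 25.0% becomes 23.8% once time or the interaction must be significant. Removing the 2.3% with a significant interaction leaves 21.5%.

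**Step 3: what happens under a better gate.** If per-group tests ran only after a significant group × time, the same collagen-only pattern would occur in 1.8% to 2.4% of cases for d from 0.3 to 0.9. The group × time test is significant in 4.9% to 5.1% throughout, as it should be.

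**Step 4: number of outcomes.** Table 1 lists nine primary outcomes for men and seven for women. Leaving out cross-sectional area and rate of torque or force development, which have three factors, seven and five remain. If each had d between 0.5 and 0.9, the expected number of such patterns would be 7 × 0.158 = 1.1 to 7 × 0.215 = 1.5 in men, and 5 × 0.158 = 0.8 to 5 × 0.216 = 1.1 in women.

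**The case against.** The strongest reply is that the harm is inferred. The SAP does test group × time for the two-way outcomes, and interactions in the three-way models, so the test that answers the research questions is planned. It does not say that paired tests are run separately by group after a time effect, or that a within-group P value counts for collagen. This stands in part: the comparisons are not named, so the calculation is conditional on the natural reading. It does not remove the fault, because the trigger is stated and nothing confines collagen conclusions to the interaction.

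The words on main effects also have an innocent use. With three tendon locations or three time-windows, a significant main effect is ordinarily followed by paired comparisons between levels, for which a paired t-test is suitable. This stands. A reader might infer that a location or time-window effect opens six pre-post tests, three levels in two groups. The wording permits that but does not call for it, so no figure is put on it here.

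A reader might also infer that every outcome reaches the post hoc step, or that the false-positive rate for collagen rises from 5% to about 20%. Neither is supported. A main effect or interaction must first be significant; at d = 0.5 and n = 10 the time effect is significant in only 56% of trials. The table gives the frequency of a pattern that misleads if misread, not the error rate of the interaction test.

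**Conclusion.** The concern holds in a conditional form. A main effect alone can open unadjusted paired t-tests, although the trial's questions are answered only by interactions involving group and time. If the tests are run by group and collagen has no effect, the collagen-only pattern with a null interaction appears in about 16% to 22% of cases per outcome for training effects of 0.5 to 0.9 SD of change. It falls to about 7% to 8% at 0.3 SD, 4.3% to 6.5% at 1.2 SD, and 1% or less at 1.5 SD.

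These figures rest on equal group sizes, normal change scores, two-sided tests and an unstated training effect. A flat rate of one in five would therefore be too strong. Nor do the documents contain a collagen conclusion drawn from within-group tests; they leave room for one.

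**What to change.** Replace the follow-up sentence with:

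> The collagen effect is judged only by the group × time interaction (for tendon cross-sectional area and rate of torque or force development, also by group × time × location or time-window). Pre-post comparisons by group are made only after a significant interaction involving group and time, and are Holm-adjusted within outcome. A significant time main effect is reported as the pooled pre-post change. A significant location or time-window main effect may be followed only by Holm-adjusted paired comparisons between levels. A group main effect opens no paired tests. Within-group P values are not used to infer a collagen effect.

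Table 1 places the analyses before the end of September 2023 and the document is dated April 2024, so this cannot be prespecified now. Apply it as the reporting rule, state which paired comparisons were actually run, and check that no reported collagen conclusion rests on within-group tests where the interaction was not significant.

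The cost is a change of wording and a check of reported results; no new data are needed. The downside is fewer significant within-group results to report.

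### All 12 outcomes are primary, giving 9 group × time tests in men and 7 in women, each at P < 0.05, with no multiplicity control and no rule for what supports a collagen conclusion

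*Combined protocol and SAP*

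**What the plan says.** Under Outcome measure information, "Table 1. Outcome measures by study arm" has 12 rows, and every row is marked primary. Four outcomes are shared by both arms, five are measured in men only and three in women only.

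The SAP states: "The analyses of data collected from each arm were performed independently". Each outcome has a two-way ANOVA with group, time and their interaction. The exceptions are tendon cross-sectional area and rate of torque or force development, which have three-way ANOVAs that add location or time-window.

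The only statement about error is "The level of statistical significance was set at" P < 0.05. On follow-up tests the SAP says: "When significant main effects or interaction effects were observed, paired t-tests were used for post hoc pairwise comparisons". It names no single lead outcome, no testing order and no adjustment, either across outcomes or for the follow-up tests.

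The Brief Summary poses three questions. One concerns tendon properties. The second asks: "Does resistance training with hydrolyzed collagen ingestion lead to greater changes in muscle size than resistance training alone". The third asks whether the combination will "lead to greater increases in strength and power compared to resistance training alone in middle-aged, healthy men and women". The Detailed Description adds that if the supplement "leads to greater improvements in tendon size, stiffness, strength and/or power, this" "will allow us to recommend this type of intervention to middle-aged athletes/trainees".

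**The concern.** The 0.05 level applies to each test, and the documents state no overall error rate. With nine or seven outcomes of equal rank in an arm, one isolated P < 0.05 is weak evidence that collagen did anything. Nothing in the plan tells the reader so, or says how many results, or which ones, would justify a conclusion.

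The follow-up rule adds a second route to a false impression. A main effect of time is enough to trigger paired t-tests, and twelve weeks of resistance training can produce a time effect in both groups. If the follow-up then tests pre versus post within each group, a report that the collagen group gained and the placebo group did not can arise when both truly gained equally. At stake is a recommendation to middle-aged athletes and trainees.

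**Working it through.** The documents give no overall error rate or power figure to reproduce, so the check starts from Table 1 and the SAP.

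**Inputs from the documents**
- Men, 9 outcomes: vastus lateralis thickness, pennation angle, tendon cross-sectional area, countermovement jump, tendon stiffness, isometric torque, rate of torque development, squat 10-repetition maximum, broad jump.
- Women, 7 outcomes: thickness, pennation angle, tendon cross-sectional area, countermovement jump, isometric force, rate of force development, 20-metre sprint.
- Analysed: 20 men and 22 women. Level: 0.05 per test.

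**Assumptions, because the documents give no figure**
- Groups of 10 + 10 men and 11 + 11 women; matching ignored.
- Collagen affects no outcome.
- Equal correlation between outcomes within an arm, from 0 to 0.7.
- One group × time test per outcome. With two groups and two times this is the same as a two-sided t-test on change scores.

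**Step 1. At least one false result, either direction**
- Independent outcomes: men 1 − 0.95^9 = 0.370; women 1 − 0.95^7 = 0.302.
- Simulation (100,000 trials) at correlation 0.3 / 0.5 / 0.7: men 33 / 28 / 21%; women 27 / 24 / 18%.

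At a given correlation these are minimum figures. The two three-way ANOVAs each add a group × time × location (or time-window) term. That makes 9 + 2 = 11 and 7 + 2 = 9 interaction tests, or 1 − 0.95^11 = 43% and 1 − 0.95^9 = 37% if independent.

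**Step 2. At least one false result in collagen's favour**

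One direction of each outcome is treated as favourable, although the documents name none for pennation angle.
- Independent: men 1 − 0.975^9 = 0.204; women 1 − 0.975^7 = 0.162.
- Correlation 0.5, simulated: about 14% and 12%.

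**Step 3. By research question, collagen's favour, correlation 0 to 0.5**

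The assignment of outcomes to questions is mine; pennation angle is left out.
- Strength and power: men, 5 tests, 1 − 0.975^5 = 11.9%, falling to 9%; women, 4 tests, 1 − 0.975^4 = 9.6%, falling to 8%.
- Tendon: men, 2 tests, 1 − 0.975^2 = 4.9%, changing little; women, 1 test, 2.5%.
- Muscle size (thickness): 1 test, 2.5% per arm.

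**Step 4. Paired follow-up tests**

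Both groups have the same true gain, in units of the SD of change (200,000 trials). The event is a significant time effect, with a significant pre–post gain in collagen but not in placebo.

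| True gain (SD) | Men | Women |
|---|---|---|
| 0.3 | 8% | 8% |
| 0.5 | 18% | 19% |
| 0.7 | 24% | 24% |
| 1.0 | 16% | 13% |
| 1.5 | 1% | 1% |

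If the within-group tests follow only a significant group × time result, the figure is about 2% or less per outcome. That is already inside the 5% error of the interaction test.

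**Step 5. Effect of Holm within each arm**
- First-step thresholds: 0.05/9 = 0.0056 (men) and 0.05/7 = 0.0071 (women).
- Error per arm: 4–5% at correlation 0.5 to 0. Across both arms: 8–10%, with 1 − 0.95² = 9.75% if each arm is held at 5%.
- Difference in change detectable with 80% power at the first step: men from 1.32 to 1.81 SD; women from 1.26 to 1.66 SD. For the difference that had 80% power at 0.05, power falls to about 45% and 50%.

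**The case against.** **The larger percentages overstate the risk of a false benefit.** A reader might take 28–37% in men as the chance of wrongly claiming that collagen helps. It is not: it counts both directions, pools all outcomes and assumes that collagen affects none of them. The collagen-favouring figures are about half. This objection stands, and both sets are needed.

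**The three research questions could be three families.** On that view tendon and muscle size stay at about 5% or less per arm and only strength and power is inflated. This is a fair alternative, and the choice of family is partly judgement. But the SAP defines no families at all, so it does not rescue the plan as written.

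**Paired t-tests might compare the groups.** It is tempting to say that they never can. The Arm 1 description says that the men were pair-matched before allocation, and Arm 2 is described as identical, so a paired test across matched pairs is conceivable. The SAP describes no such test, and its baseline comparisons use independent t-tests. The safe statement is that, as ordinarily applied, pre versus post, paired tests do not compare collagen with placebo.

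**The follow-up tests may be harmless.** Location and time-window have three levels, where paired comparisons are a usual follow-up. The 8–24% at gains of 0.3 to 1.0 SD requires within-group testing after a time effect alone. The SAP's wording permits that but does not say it was done.

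**Any adjustment now is retrospective.** True. It can limit what is claimed; it cannot create prespecified status.

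**Conclusion.** The point holds. Every outcome is primary, each is tested at 0.05, and no adjustment or decision rule is stated. If collagen has no effect on any outcome, the chance of at least one false group × time result in either direction is about 28–37% in men and 24–30% in women at correlation 0.5 to 0, and 21% and 18% at 0.7. In collagen's favour only, it is about 14–20% and 12–16% at correlation 0.5 to 0. The inflation sits mostly in strength and power, at 8–12% per arm. Correlation and group sizes are assumed, but no value in the range examined brings the two-direction figure for an arm near 5%.

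The follow-up problem is conditional: it is material if pre–post tests are run within each group after a time effect alone, and negligible if they follow only a significant interaction.

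A reader might also infer that the Detailed Description sets a success rule under which any one gain in tendon size, stiffness, strength or power justifies a recommendation. The sentence is rationale, not a decision rule, so no error rate should be built on it. Nor do these figures show that any reported result is false. The matter should be fixed in reporting.

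**What to change.** - Base any collagen conclusion only on the between-group comparison of change, that is, the group × time term, including that term in the three-way ANOVAs.
- Report every outcome with the between-group difference in change, its confidence interval, and unadjusted and Holm-adjusted P values within each arm (9 tests in men, 7 in women).
- Say why the arm rather than the research question was taken as the family. The separate analyses by arm are one reason. State that error across both arms can still reach about 10%.
- Report the location and time-window interactions as planned, but do not count them as separate support.
- State which pairs the paired t-tests compare, and treat pre–post tests as description only.
- Do not rest a recommendation on one isolated unadjusted P < 0.05.
- State that the adjustment was set after the analysis (the document is dated 04/22/2024; Table 1 has analysis running to September 2023). It limits interpretation and does not confer prespecified confirmatory status.

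The cost is SAP and report wording plus adjusted P values, with no new data. The price is the power loss shown in Step 5. A tendon effect confined to one region would be reported but would not count as support on its own.
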